1.1.3. Gaps in Optimal therapy selection and sequencing

Figure 2 presents an algorithmic overview of the investigation and treatment of GEP-NETs (the most common NET subtype) [17]. For low to intermediate grade NETs, surgery remains the mainstay of treatment and the requirement for adjuvant therapy is questionable [18-20]. However, as over half of GEP-NETs present with metastases at the time of diagnosis, they are not considered candidates for curative surgery, and so many are offered some form of long-term medical treatment for symptom relief and tumor growth suppression. Somatostatin analogues (SSAs) are established first-line agents for low-grade GEP-NETs, largely given their demonstrated improvements in overall survival in two placebo-controlled randomized trials ([PROMID](#) and [CLARINET](#)) [21, 22]. However, there are no clear consensus guidelines as to the optimum sequencing of other therapeutic options [17, 21, 23-27]. Systemic, non-liver directed therapies may include peptide receptor radionuclide therapy (PRRT), interferon alpha, everolimus (an mTOR inhibitor), sunitinib (a tyrosine kinase inhibitor), bevacizumab and cytotoxic agents [17]. Liver-directed therapies include ablative therapy, transarterial embolization and chemoembolization, and internal radiation therapy with yttrium-90 coated microspheres [28]. Interestingly, an assessment of the clinical benefit of systemic treatments in GEP-NETs found that currently used treatments had low health benefit scores according to the ASCO-NHB, and none could be graded as meaningfully clinically beneficial according to the ESMO-MCBS [29]. Therefore, one of the greatest challenges in the current NET oncology management landscape is how best to sequence these many therapeutic options (if warranted at all), and how to tailor treatment selection on the basis of the individual characteristics of the tumor and patient.

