1.1.5. Significance

The lack of consensus guidelines as to the optimum sequencing of treatments, means that NET patients and clinicians are confronted with very real and difficult treatment decisions. Due to the relatively small number of patients included in clinical trials related to the important NET subgroups previously highlighted, it is difficult to evaluate both the factors that may affect treatment receipt and their influence on patient-reported outcomes and prognosis. Our large study's rigorous collection of symptom, tumor and treatment burdens and their impacts on HRQoL indicators will improve patient outcomes through the application of more informed treatment sequencing and monitoring of disease burden. While patients with a localized, resectable tumor may go straight to surgery, those with locally advanced or synchronous metastatic disease may benefit from the delivery of a more complicated series of treatments which are somewhat personalized to the preference of the patient and the proliferative profile of their tumor.

The NET-PRO study will address at least three large challenges patients face in what they are offered for the current management of NETs.

- a. Unknown optimal sequencing of systemic and non-systemic therapeutic options. Because clinicians currently do not understand what options (with the lowest toxicities) should be tried first given a patient's particular proliferative tumor burden, they are not able to provide evidence-based recommendations. Our communications with NET patients and our patient advocacy partners strongly attest that this is a research question that is important to them. This is what is driving our study aim 3, which will compare the effectiveness of various PPRT treatment combinations and sequences on outcomes of renal toxicity and radiographic evidence

of disease progression. This prospective CER study may ultimately help improve the standardization and optimization of PRRT procedures [43], increasing therapy effectiveness, driving adoption of protective interventions, and improving patient outcomes.

- b. Treatment of grade 3 well differentiated NETs is an area of controversy. Data from two of our participating sites (Iowa and Vanderbilt) is supportive of earlier initiation of PRRT in these patients (neo-adjuvant setting), and a large CER study with targeted chart review and electronic medical record (EMR) data would be able to assess progression-free survival outcomes.

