6.1. EMR data – Clinical and billing data from the PCORnet CDM

The PCORnet CDM is a key component of the PCORnet Distributed Research Network infrastructure, and will serve as the primary data source for the NET-PRO study. In late 2023, the UICC will request data from sites on all enrolled subjects. Data will include demographics, toxicity outcomes, vitals and vital status, treatments, laboratory tests and results, health conditions (comorbidities), tumor characteristics (from tumor registry variables/tumor tables in the CDM), disease status, and encrypted IDs used to link patient care across sites. The data will cover the period two years prior to the subject's NET diagnosis through approximately 36 months after the date they joined the study. Note, as per the inclusion criteria, we will not be excluding patients who do not have 2 years of look-back data prior to their diagnosis date. Table 2 summarizes the variables that will be obtained from the CDM. The specific code lists for derivation of these variables in the CDM will be later specified and distributed to sites.

Table 2: Patient, clinical and tumor variables that will be measured from the CDM

Concept/variable		CDM Tables
Demographics	Date of birth, sex, Hispanic, Race	Demographic Table
Toxicity outcomes	Acute renal failure, dialysis, liver failure	Diagnosis Table
Vitals	Height, weight, systolic and diastolic blood pressure, smoking	Vitals Table
Cancer Treatments	Somatostatin Analogues (SSAs) (octreotide, lanreotide, pasireotide) Bevacizumab, Cytotoxic chemotherapy, Everolimus, Interferon alpha, Hepatic Artery Bland-, Chemo- or radioembolization, PRRT -Lutetium Lu-177 dotatate, PRRT-Yttrium-90 Dotatoc, Small molecule TKIs, Telotristat ethyl)	Dispensing, prescribing, procedures, and medications administered Tables
Lab values	Alanine transaminase (ALT), Albumin and Microalbumin Albumin/Creatinine and Microalbumin/creatinine Ratio, Alkaline phosphatase (ALP), Aspartate transaminase (AST), AST/ALT ratio, Blood Urea Nitrogen, Chromogranin A, Cystatin C, Hemoglobin, Ki-67, Lymphocytes, Pancreastatin, Serum or Blood Creatinine, Somatostatin, Total Bilirubin	Lab results

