- 2) **European Organization for Research and Treatment of Cancer - Quality of Life Questionnaire - Neuroendocrine Carcinoid Module (EORTC QLQ-GI.NET21)** The EORTC QLQ-C30 can be used in conjunction with the EORTC QLQ-GI.NET21 specific questionnaire, which comprises a total of 21 items: four single-item assessments relating to muscle and/or bone pain (MBP), body image (BI), information (INF) and sexual functioning (SX), together with 17 items organized into five proposed scales: endocrine symptoms (ED; three items), GI symptoms (GI; five items), treatment-related symptoms (TR; three items), social functioning (SF21; three items) and disease-related worries (DRW; three items). Responses to the QLQ-GINET21 will be linearly transformed to a 0-100 scale using EORTC guidelines, with higher scores reflecting more severe symptoms.

[Time Frame: Change in mean score across baseline, 6, 12, and 18 month time points.]

- 3) **Sequencing of treatment regimens from electronic medical records.** This will involve identifying which treatments a patient used during their follow-up, and also in what order they received treatment. Dates and types of therapy initiated will be pulled from each patients EMR in reference to the patient’s index date (date of diagnosis). We will also be asking patients about their treatments (self-reported) in the baseline survey to ascertain potential missed therapies in the EMR. We will be comparing the frequency (N) and proportion (%) of use of a variety of therapies (i.e.: SSAs, bevacizumab, cytotoxic chemotherapy, everolimus, Interferon alpha, embolization, PRRT, small molecule TKIs) and the effects of their ordering/sequencing on outcomes of symptom burden and HRQoL.

[Time Frame: Up to 5 years, baseline to end of follow-up]

- 4) **Renal function.** Glomerular filtration rate (GFR) is the best overall index of kidney function. Normal GFR declines with age, and varies according to sex, race and body size. We will calculate creatinine clearance loss [54] by combining individual level CDM and enrollment questionnaire data on sex, race, height, weight and serum creatinine mg/dl laboratory values at regular intervals before and after PRRT cycles until the end of follow-up.

[Time Frame: Change in eGFR from baseline to end of follow-up.]

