8. COMPARATORS

This section details the main independent variables that will be used to compare outcomes of HRQoL, sequencing of treatment regimens and kidney function.

In all 3 study aims we will be comparing both the frequency of use of first, second and third line and beyond therapies (SSAs, bevacizumab, cytotoxic chemotherapy, everolimus, Interferon alpha, embolization, PRRT, small molecule TKIs) and the effects of their ordering/sequencing on other secondary outcomes (i.e.: symptom burden, survival and adverse toxicity). These interventions have been selected as they are listed as potential biological therapies, liver directed therapies or chemotherapies that are routinely available to NET patients, and for which there is no clear consensus as to the effectiveness of their ordering (or concomitant use).

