9.3. Addressing confounding

With a large, proposed sample size of approximately 3,000 patients, we will minimize the effects of confounding on treatment effect estimates by adjusting for factors associated with treatment selection within the context of multivariable models. Known and hypothesized factors associated with treatment selection include but are not limited to the following: sociodemographic (age, sex, race, ethnicity, marital status, income), health status (BMI, smoking history, comorbidities), disease (site, stage, grade, nodal status), prior therapy use (PRRT, everolimus, sunitinib, liver-directed therapies, chemotherapy, surgery), and patient-reported preferences, attitudes, beliefs and experience of care. Determination of confounding factors that may warrant adjustment will be guided by the results from the multinomial logistic regression models evaluating factors associated with selection of treatment regimens (Aim 2). Furthermore, the use of time-dependent variables for treatment and potential confounders (where appropriate) will minimize the effects of survivor treatment selection bias.

As a novel project aimed to evaluate the complex interplay between patient, disease, and treatment factors on toxicity, HRQoL, and survival outcomes, the statistical analysis plan will be refined once descriptive information from Aims 1 and 2 is available for consented patients. For example in Aim 3, PRRT sits amongst a growing number of therapeutic options in metastatic well-differentiated NETs, including pharmacological (i.e.: mTOR inhibitor everolimus and the tyrosine kinase inhibitor sunitinib), hormonal and liver-directed therapies (i.e.: embolization (bland, chemo, radio)), and surgical approaches. Therefore, we need to be mindful of this multimodal treatment algorithm wherein patients may undergo a variety of treatment options at tumor progression(s).

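### Surgery and ablation have no named, dated place in the treatment data or the sequence lists, although prior surgery is a planned confounder and first-line therapy is undefined without a rule for it

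*Protocol*

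**What the plan says.** Treatment is made operational in three places in the protocol, and surgery is in none of them.

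- Section 7.1, item 3 (sequencing of regimens, the Aim 2 primary outcome in Table 4) compares use and ordering of a "variety of therapies (i.e.: SSAs, bevacizumab, cytotoxic chemotherapy, everolimus, Interferon alpha, embolization, PRRT, small molecule TKIs".
- Section 8 names the comparators for all three aims as "first, second and third line and beyond therapies (SSAs, bevacizumab, cytotoxic chemotherapy, everolimus, Interferon alpha, embolization, PRRT, small molecule TKIs", the same eight classes.
- Table 2 in section 6.1, under Cancer Treatments, covers SSAs, "Bevacizumab, Cytotoxic chemotherapy, Everolimus, Interferon alpha, Hepatic Artery Bland-, Chemo- or radioembolization", PRRT by isotope, small molecule TKIs and telotristat.

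Ablation is also absent from all three.

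Other sections give surgery a central role. Section 1.1.3 states: "For low to intermediate grade NETs, surgery remains the mainstay of treatment and the requirement for adjuvant therapy is questionable". Section 1.1.5 says that "patients with a localized, resectable tumor may go straight to surgery". Section 9.3 lists, among factors associated with treatment selection, "prior therapy use (PRRT, everolimus, sunitinib, liver-directed therapies, chemotherapy, surgery". Sections 1.1.4 and 1.1.5 present neoadjuvant PRRT in grade 3 tumors as a motivating question. Section 1.1.3 places ablative therapy among the liver-directed options.

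**The concern.** The cohort is every newly diagnosed GEP or lung NET in adults, at any stage (section 4.2), so it includes patients whose first treatment is an operation. Aim 1 describes regimens by line. Aim 2 models selection of first-line and later regimens. In section 7.2, item 3, time to first progression starts when first-line therapy is initiated. All three need a rule for where surgery stands, and the protocol gives none.

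Two things are at stake. The first is adjustment: a confounder that is not collected with a date cannot be handled as prior therapy or as a time-dependent variable. The second is comparability: a first-line group can mix patients who start a drug at diagnosis with patients who start the same drug after resection and recurrence. These two groups can be expected to differ in stage at diagnosis and in time since diagnosis.

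This cannot be left wholly to an analysis plan. The protocol fixes what is collected, by a data request to sites in late 2023 (section 6.1) and a chart review at a single time point (section 6.2). An analysis plan cannot use operations that were never requested.

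**Working it through.** The protocol gives no figure to reproduce, so the check is a comparison of sections.

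**1. Is surgery a named variable anywhere?**

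- Table 2, Cancer Treatments: drugs, embolization and PRRT. No resection, no ablation.
- Table 2, Tumor Characteristics (registry): grade, stage, nodal status and other pathological features. No surgery field is named.
- Table 3 (surveys): self-reported treatments at baseline and follow-up, in general terms.
- Section 6.2 (chart review): disease status, under-populated CDM variables, and other clinical or pathological characteristics. Surgery is not named.
- Section 9.5: chart review fills variables that are insufficiently populated in the CDM. Surgery was never specified as one of them.
- Section 6.1: code lists are still to come, but for the variables in Table 2.

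Section 9.1 draws covariates from Tables 2 and 3. Prior surgery, required by section 9.3, could therefore enter only through the general self-report item.

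**2. Does the stated reason for the list explain the gaps?** Section 8 limits the list to biological, liver-directed and chemotherapy options whose ordering is unsettled. That can explain leaving out surgery. It cannot explain leaving out ablation, which section 1.1.3 classes as liver-directed.

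**3. What happens to first line?** Take three illustrative patients and apply only the listed classes.

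- A: resected in 2019, recurrence, SSA started in 2022. The first listed therapy is the SSA in 2022.
- B: metastatic at diagnosis in 2019, SSA started in 2019. The first listed therapy is the SSA in 2019.
- C: resected in 2019, nothing further. There is no listed therapy.

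A and B fall into the same first-line SSA group. For C, neither the first line nor the start of time to first progression is defined. For A, if the recurrence is abstracted as a progression, it precedes the start of that clock.

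**4. What is unaffected?** PFS and OS run from diagnosis (section 7.2, items 3 and 4), and the Prentice-Williams-Peterson model uses the gap from initial diagnosis to first progression (section 9.1.2). Their time origin does not depend on how lines are numbered.

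**5. Can the number affected be bounded?** Section 1.1.1 gives metastases at diagnosis in up to 40% of NETs: 3,010 × (1 − 0.40) = 1,806 non-metastatic as a minimum, if the cohort resembles all NETs. Section 1.1.3 gives over half of GEP-NETs: 3,010 × (1 − 0.50) = 1,505 as a maximum, if that figure is applied to the whole cohort, lung included. A minimum of 1,806 and a maximum of 1,505, from different populations, do not form a range. Neither counts resected patients, because no resection rate is given.

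**The case against.** A reader might infer that lines are misnumbered, that resected patients will appear untreated or drop out of the first-line model, and that the sequence comparisons are therefore confounded. The document does not support that much.

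- No definition of a line includes surgery. Section 8 gives a rationale under which numbering only non-surgical lines may be deliberate, and on that reading the 2022 SSA is correctly the first such line.
- Other sources may capture operations. Section 7.1, item 3 uses the baseline self-report to find therapies missed in the EMR. Appendix B says registries abstract treatment. Section 10.2 says most sites will find a direct load of all registry elements most efficient. Every enrolled subject has a chart review, on a form still to be developed.
- Section 9.1.2 does not list the outcome categories of the multinomial model. A surgery-only category is not excluded and is normal content for an analysis plan.
- Section 9.3 intends to adjust for stage, grade, nodal status and prior surgery, which goes some way to separating patients A and B.

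These points stand and limit the conclusion, but they do not remove it. None of the alternative sources names surgery, requires its date or gives it a place in the sequence. The essential registry elements are still to be determined (section 10.2), and Appendix B reports that only about two-thirds of eligible cases at Iowa are in the registry. Adjustment for prior surgery presupposes that it is collected. A deliberate choice to number non-surgical lines would still need to be stated, because section 7.2 hangs an endpoint on first-line therapy.

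**Conclusion.** The concern holds in limited form. Resection and ablation are missing from the treatment data pull, the primary sequencing list and the comparators. This conflicts with the role the protocol gives surgery in sections 1.1.3, 1.1.5 and 9.3, and with its own description of liver-directed therapy. A planned confounder lacks a named, dated source. First-line therapy and the start of time to first progression are undefined for patients treated with surgery first or only. The neoadjuvant PRRT question also needs operation dates to be answerable.

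The size cannot be stated: the document supports no count of affected patients, and a figure of roughly 1,500 to 1,800 should not be used. The conclusion assumes that the three lists are followed as written. It does not assume that surgery must count as a line, or that every operation would be lost. It should be settled before the data request, because a primary outcome and a planned adjustment depend on it.

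**What to change.** Before the data request:

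- Add surgical resection (primary tumor, metastasectomy) and ablation, each with type and date, to the Cancer Treatments row of Table 2, drawing on the procedures table and the registry treatment field. Add the same items to the chart-review form.
- Reconcile section 6.1 (Table 2), section 7.1 item 3, section 8 and section 9.3 so that they carry the same treatment list.
- Record surgery as its own step in the sequence. Label the numbered lines as non-surgical lines, with prior resection as a stratum or covariate.
- State how first line, and the start of time to first progression, are defined for patients with surgery first or only.
- Keep surgery only and no treatment as categories in the description of first treatment and in the selection model.

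The cost is some extra codes in a query whose code lists are still open, a few chart-form fields and short protocol wording. The statistical downside is more treatment categories and so thinner cells in the multinomial models.

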7.2. Secondary Outcomes

- 1) **Norfolk Carcinoid Symptom Score.** The Carcinoid Symptom Score [49] contains 13 questions, where question 1 has 3 queries about flushing, with a maximum of 3 points; question 3 has 4 items inquiring about respiratory symptoms, with a maximum score of 4. There are 3 questions about gastrointestinal symptoms for a total of 3 points, 3 questions related to physical functioning for a total of 3 points, and 3 questions related to cardiovascular disease for a total of 3 points; the remaining 2 questions are about family and personal medical history. The answers to the questions are quantified as “0” (no symptom) and “1” (symptom present), so the higher the score the worse is the symptom burden, from a score of “0” to “18.”
[Time Frame: Change in score across baseline, 6, 12, and 18 month time points.]
- 2) **Experiences with cancer care (from CANCORS).** 13 items assess patients' experiences with interpersonal aspects of cancer care [53], including physician communication (five items), nursing care (two items), and coordination and responsiveness of care (six items). The scores in each domain are converted to 100-point scales, with 0 representing the worst possible care and 100 representing optimal care. Patients can also rate the overall quality of their health care since cancer was diagnosed on a 5-point scale ranging from excellent to poor.
[Time Frame: Change in score across baseline, 6, 12, and 18 month time points.]
- 3) **Progression-free survival (PFS).** Time to event data will be calculated from the index date (date of diagnosis) to the earliest of disease progression, death from any cause or end of study follow-up (12/31/2023). Acknowledging that patients may have more than one progression over the study period endpoints of median time to first progression (time from initiation of first-line therapy to progression) and time to second progression (time from second-line therapy initiation to progression) will be observed from targeted chart reviews at annual intervals. In collaboration with our clinician group we have discussed the various limitations of the application of the RECIST 1.1 criteria in NETs. These limitations include an overemphasis on tumor progression (given the low proliferation rate of GEP-NETs, monitoring changes in tumor size is suboptimal), and RECIST 1.1 criteria do not reflect overall tumor load or response to therapy in metastatic patients (i.e.: issues with clinical significance of radiologic progressions). Optimizing the management of NET patients therefore requires considering clinical, biological, and pathological aspects of the tumor. We have therefore chosen to categorize disease progression as DISEASE CONTROL (complete or partial response & stable disease), PROGRESSION (with no treatment change), PROGRESSION (with treatment change), and INDETERMINATE. This clinician-anchored approach has been found to be an optimal and valid method (versus RECIST1.1) for evaluating real-world tumor burden endpoints from EMR data [55].
[Time Frame: median time to progression, assessed annually via chart review]
- 4) **Overall Survival (OS).** Time to event data will be calculated from the date of diagnosis (index date) to the date of death from any cause, or end of study follow-up (12/31/2023). Death and vital status (death date, cause of death) will be pulled from the death table, and death cause table in the CDM. This data may be supplemented from site linkage to the social security death index or cancer registry sources (where possible). Given the prospective nature of the study we also have potential for passive surveillance/follow-up with participant/next of kin with information collected on our follow-up questionnaires.
[Time Frame: Up to 5 years]
- 5) **Adverse toxicities.** We will assess incident acute renal failure, dialysis and liver failure during study follow-up (from diagnosis codes in the CDM). The occurrence of these events will be compared in reference to the treatment regimens received.
[Time Frame: Up to 5 years]

Table 4: Overview of Primary and Secondary outcomes for NET-PRO by project aims

Primary or Secondary	Name of Outcome	Specific Measure(s)/ Instrument(s) to Be Used	Timepoints (mths)	PROMIS and/or Core Outcome Set ?	Powered Yes/No/NA
Aim 1					
Primary	Health related Quality of Life (HRQoL)	EORTC QLQ-C30 EORTC QLQ-GI.NET21	0, 6, 12, 18	Yes	Yes
Secondary	Symptom inventory	Norfolk Carcinoid Symptom Score [49] Norfolk Carcinoid Symptom Score [49]	0, 6, 12, 18	No	No
Secondary	Experiences of care	Physician communication, coordination and responsiveness of care [62]	0, 6, 12, 18	No	No
Aim 2					
Primary	Sequencing of treatment regimens	-	0-60	No	Yes
Secondary	Progression-free survival	Time to event (Categorization of stable disease, disease progression with no change in treatment, disease progression with changes in treatment, and indeterminate)	0-60	No	Yes
Secondary	Overall survival	Time to event	0-60	No	NA
Secondary	Adverse toxicities	Incident acute renal failure, dialysis and liver failure during follow-up	0-60	No	NA
Aim 3					
Primary	Renal function	Creatinine clearance loss (per/Yr)	0, 6, 12, 18	No	Yes
Secondary	Adverse toxicities	CDM diagnosis codes for acute renal failure, dialysis and liver failure during follow-up	Up to 60	No	No
Secondary	Health related Quality of Life (HRQoL)	Changes in HRQoL and symptom scores	0, 6, 12, 18	No	No
Secondary	Renal toxicity (creatinine clearance) by PRRT isotope	Creatinine clearance loss (per/Yr) 177Lu vs 90Y	Up to 60	No	No
Secondary	Renal toxicity of PRRT by primary tumor location & grade 3 disease	Creatinine clearance loss (per/Yr) GEP-NETs vs lung NETs and G3	Up to 60	No	No

NA: Not applicable

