4.2. Inclusion/Exclusion Criteria

To be eligible for this prospective cohort study subjects must meet **all** of the following criteria:

- i. Incident GEP-NET/Lung NET diagnosis*(see [Appendix A](#))
- ii. Diagnosed 01/01/2019-12/31/2023
- iii. No known prior GEP-NET/Lung NET diagnosis
- iv. Aged ≥ 18 years at diagnosis
- v. At least one site encounter within the study period of January 1, 2019 to December 31, 2023

* See [Appendix A](#) for a full list of International Classification of Diseases, Ninth Revision, Clinical Modification (ICD-9-CM), The International Classification of Diseases, Tenth Revision, Clinical Modification (ICD-10-CM) codes used to define a NET diagnosis. This appendix also lists the ICD-O-3 site codes and eligible histology codes for implementation in tumor registry data sources.

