Comorbid conditions	Chronic Pulmonary Disease, Congestive Heart Failure, Coronary Artery Disease, Diabetes with complications, Diabetes without complications, Hypertension, End Stage Renal Disease, Mild Liver Disease, Severe Liver Disease, Peripheral vascular disease, Renal Disease, Myocardial Infarction	Diagnosis Table, Conditions Table (for conditions in the 2 years prior to GEP-NET/lung NET diagnosis)
Vital status	Vital status (death date, cause of death)	Death Table. Death Cause Table – supplemented with local site linkages and patient survey data

Linkage	Patient ID, token	Hash token table (Datavant link module)
Tumor Characteristics	Tumor characteristics (NAACCR required variable list (i.e.: tumor grade, stage, nodal status and other relevant pathological characteristics))	Tumor Table or cancer registry data sources

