6.2. EMR data – Abstracted medical record data (per chart review)

Targeted chart reviews will be conducted at one point in time (towards the end of study follow-up period i.e.: Dec 2023) for all subjects enrolled in NET-PRO. Chart reviews will be undertaken to evaluate the following items:

- 1) Disease status (four-category variable defined below)
- 2) Clinical variables found to be insufficiently populated in the CDM
- 3) Other Clinical/pathological characteristics not recorded elsewhere (examples below)

The UICC has budgeted \$100 for chart abstraction for each case. In consultation with the clinician group, the consensus was that application of the RECIST criteria may be impracticable given current NET-PRO resources. Targeted chart abstraction will include a four-level categorization of disease status:

- 1) Disease control
- 2) Progression (no change in treatment)
- 3) Progression (with changes in treatment)
- 4) Indeterminate.

It was agreed that the clinical assessment and plan, would be the best source for identification of disease status for chart abstractors.

Other variables that may be selected for targeted chart review include clinical variables found to be insufficiently populated in the CDM. These may include interval lab values related to serum creatinine, BUN and eGFR (related to ascertainment of kidney toxicity for Aim 3) before and after PRRT cycles. It will also be important to collect tumor variables (i.e.: stage, grade, nodal status) for patients who were not identified from institutional tumor registries. An additional target for chart review may be other prognostic clinical/pathological characteristics not recorded elsewhere in the CDM or cancer registry data sources. For example information on mitotic count, chromogranin A (CgA) and Ki-67 proliferation index.

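### PFS without a recorded event runs to 12/31/2023 although progression is seen only in the enrolling site's chart, so time after leaving site care counts as progression-free; for OS this matters only where death capture is incomplete

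*Protocol*

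**What the plan says.** Section 7.2, item 3, measures PFS from diagnosis "to the earliest of disease progression, death from any cause or end of study follow-up (12/31/2023"). Item 4 measures OS from diagnosis "to the date of death from any cause, or end of study follow-up (12/31/2023"). Neither item stops time at a last assessment, last contact or last date known alive, and section 9 of the protocol adds no such rule.

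The two endpoints draw on different sources.

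- **Progression.** Section 6.2 states that "the clinical assessment and plan, would be the best source for identification of disease status for chart abstractors". It also says "Targeted chart reviews will be conducted at one point in time (towards the end of study follow-up period i.e.: Dec 2023"), while 7.2 speaks of annual intervals. No source of progression outside the site's chart is named.
- **Death.** The CDM death tables are the base. Section 7.2 adds that "This data may be supplemented from site linkage to the social security death index or cancer registry sources (where possible"), and that "we also have potential for passive surveillance/follow-up with participant/next of kin". Table 2 describes vital status as "supplemented with local site linkages and patient survey data". Section 5.9 has sites record dates of death in the tracking database.

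Eligibility (section 4.2) asks only for "At least one site encounter within the study period of January 1, 2019 to December 31, 2023". Continuing care at the site is not required.

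**The concern.** A progression can enter the data only while the patient is being assessed at the enrolling site. Once that stops, the stated rule still adds event-free time up to the fixed date. In a Kaplan-Meier or Cox analysis such a patient stays in the risk set but can no longer have a recorded progression. The estimated hazard is then too low and PFS too long.

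If loss from site care differs between regimens, the regimen with more loss looks better for that reason alone. Section 9.2.2 names the effect of treatment sequences on PFS as the primary objective of Aim 2, so this comparison matters to the study. The gap-time model in 9.1.2 would carry the same end date into later progressions.

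**Working it through.** **1. The plan's own figures.** Table 6 assumes 48 months of uniform accrual, 12 months of follow-up, no loss, and a two-sided 5% log-rank test by the Lakatos method. With exponential PFS it reproduces:

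| Medians (months) | n per arm | Stated | Recomputed |
|---|---|---|---|
| 12 v 24 | 45 | 0.79 | 0.795 |
| 12 v 24 | 50 | 0.83 | 0.835 |
| 24 v 36 | 175 | 0.80 | 0.801 |
| 24 v 36 | 190 | 0.83 | 0.832 |

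The table is correct on its terms, and those terms include that nobody is lost.

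**2. PFS under the stated rule, loss from diagnosis.** The true median of 24 months is taken from Table 6. The annual loss p of 5, 10 or 20% is assumed. Loss is taken as independent of prognosis, with every later event unseen.

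- Event hazard per month: h = ln 2 / 24 = 0.02888.
- Loss hazard per month: l = −ln(1 − p)/12 = 0.00427, 0.00878, 0.01860.
- Chance that an event is recorded by month t: [h/(h + l)] × [1 − exp(−(h + l)t)].
- Setting this to 0.5 gives the apparent median t = −ln[1 − 0.5(h + l)/h]/(h + l).

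For p = 10%: h + l = 0.03766 and 0.5 × 0.03766/0.02888 = 0.652, so t = −ln(0.348)/0.03766 = 28.0 months. For p = 5%, t = 25.7. For p = 20%, t = 36.3.

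A simulation of 400,000 patients with administrative follow-up uniform on 12 to 60 months agrees:

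| True median | Stated rule, 5/10/20% loss | Stopped at last contact |
|---|---|---|
| 12 | 12.4 / 12.8 / 14.2 | 12.0 / 12.0 / 12.0 |
| 24 | 25.8 / 28.0 / 36.4 | 24.0 / 24.0 / 23.9 |
| 36 | 40.1 / 46.3 / not reached | 35.9 / 35.8 / 36.1 |

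**3. PFS under the stated rule, loss from consent.** Table 8 projects recruitment from 4/29/2022, so time from consent to 12/31/2023 is at most about 20 months. Assume diagnosis uniform over 2019 to 2022, and consent uniform from April 2022 to December 2023 and never before diagnosis. If loss starts only at consent, the apparent median for a true 24 is about 24.1, 24.2 and 24.5 months. Delayed entry into the cohort is a separate matter and is left aside here.

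**4. Unequal loss.** Take two groups with the same true median of 24 months and loss from diagnosis. With 5% v 20% annual loss, the ratio of apparent event rates is about 0.75 in favor of the group with more loss. With 5% v 10% it is about 0.91.

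**5. OS.** Assume 5-year survival of 70%, so true 48-month OS is 0.70^(48/60) = 0.752. Under the stated rule, by share of deaths captured after the patient leaves site care:

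| Captured | 48-month OS at 5/10/20% loss |
|---|---|
| None | 0.774 / 0.794 / 0.831 |
| 50% | 0.762 / 0.774 / 0.792 |
| 80% | 0.756 / 0.761 / 0.768 |
| All | 0.752 / 0.752 / 0.753 |

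With full capture the fixed date does no harm.

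A careless repair reverses the bias. At 10% loss with 50% captured, stopping survivors at last contact while still counting linked deaths gives 0.729. With 80% captured it gives 0.716. Applying the same cut-off to deaths and survivors returns 0.752.

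**The case against.** Five points can be made for the plan.

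- **Censoring detail belongs in the SAP.** Section 13.3.1 refers to a separate SAP and 9.3 says the plan will be refined, so the fixed date could be read as an outer limit. This stands only in part. The protocol states the end point as a calendar date, and an SAP that stopped PFS earlier would depart from 7.2.
- **Disease status has an indeterminate category.** An abstractor need not record disease control for a patient with no recent assessment. That is true, but the protocol does not say how this category enters PFS time, and the end rule has no place for it.
- **Loss is not documented.** This stands. One encounter is an eligibility minimum and is not evidence of loss. The remark in Appendix B about patients seen for tests or a second opinion explains why registries miss cases; it does not describe follow-up of enrolled participants. A reader might infer that PRRT patients leave referral centers more often than patients on other regimens, but the documents contain nothing on this.
- **Death is also a PFS event and has other sources.** This stands, so treating every later event as unseen is an upper case.
- **PFS is a secondary outcome and Aim 2 is called exploratory.** This stands and lowers the severity.

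A reader might also infer that OS is overstated in the same way as PFS. The documents do not support that. Sections 5.9, 6.1 and 7.2 name sources of death that do not depend on site visits. Several are worded as optional, so completeness is unknown, but incomplete capture cannot be assumed.

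**Conclusion.** The point holds for PFS. Where a patient leaves site care and later events go unseen, the direction of the bias is upward. Its size cannot be fixed from the documents. For a true median of 24 months and assumed annual loss of 5 to 20%, the apparent median lies between about 24.1 and 36 months, depending mainly on whether loss starts at consent or at diagnosis. Some patients may leave site care before they are invited, so the truth may lie between the two cases.

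It is tempting to say that the rule creates an error as large as the 24 v 36 month contrast in Table 6. That needs 20% annual loss from diagnosis with no later event seen. It is an extreme, and the protocol itself calls the situations in that table hypothetical.

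For OS the concern is conditional: there is no bias with complete death capture, and an overstatement that grows with the share of deaths missed. All sizes assume exponential times and loss unrelated to prognosis. Severity is moderate.

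**What to change.** - **PFS (7.2, item 3).** End PFS time for patients without an event at the last documented clinical disease assessment on or before 12/31/2023. Add the date of that assessment to the REDCap chart form. Item 3 should also say whether a death found long after the last assessment counts, since the asymmetry shown for OS can arise there too.
- **OS (7.2, item 4).** Keep 12/31/2023 where death capture is complete to that date through death index, registry or equivalent linkage. Elsewhere, censor at the last date known alive and apply the same cut-off to deaths, so that deaths found later by partial linkage are not counted while survivors stop at last contact.

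The cost is a few sentences in 7.2 and one date field on a form that section 6.2.1 says is still to be developed. Because 6.2 plans a single abstraction, adding the field afterwards would mean reopening charts. The downside is less nominal follow-up and somewhat wider intervals. With 10% annual loss and proper censoring, for example, the Table 6 power of 0.80 at 175 per arm becomes 0.74. If loss is related to prognosis, censoring at the last assessment does not remove all the bias.
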